	Screen	1	2	3	4	5	6	7	8	9	10	11	12	13	14	15	16	17	18	19	20	21	22	23	24	25	26	27	28	29	30	31	32				
ALL PATIENTS																																					
Check inclusion / exclusion criteria	X																																				
Informed consent	X																																				
Optional blood sample (check consent)	X																																				
Request stored pathology samples (check consent)	X																																				
Offer OxMdG or IrMdG	X																																				
Send sample of primary cancer for KRAS analysis	X																																				
Randomisation	X																																				
Calculate GFR (if < 50 ml/min, measure GFR)	X																																				
QoL questionnaire	X																																				
CT scan (Chest, abdo, pelvis or equiv.)	X*																																				
Tumour marker (CEA or other)	X*																																				
Liver resection surgery	X*																																				
Collect pathology samples (check consent)																																					
OxMdG and IrMdG PATIENTS																																					
Check adverse events		X																																			
Clinical evaluation		X																																			
RECIST response	X																																				
NCI CTC scores		X																																			
WHO PS		X																																			
FBC, U&Es, LFTs, magnesium**		X																																			
Chemotherapy - folinic acid		X																																			
Chemotherapy - Oxaliplatin (OxMdG) or Irinotecan (IrMdG)		X																																			
Chemotherapy - 5FU		X																																			
Chemotherapy - Cetuximab (if applic.)		X																																			
Return data to UoSCTU		X																																			

Results from FBC, U&Es, LFTs required before patient attends baseline visit; delay between baseline visit to week 1 visit must be < 3 weeks if clinically acceptable; * = procedure may be performed at screening or baseline but must be within 6 weeks prior to chemotherapy; † = if raised at baseline; ** = measure in all patients showing possible symptoms of hypomagnesaemia; QoL = quality of life; NCI CTC = national cancer institute common toxicity criteria; WHO PS = world health organisation performance status; follow-up schedule (including CT scans) described section 11 should be followed after the treatment phase

4. Introduction

Background

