The type and extent of liver resection should be decided at time of randomisation and should include all the areas that have contained tumour even when there is marked tumour shrinkage or a complete radiological response. It is accepted by most liver surgeons that the benefit of neoadjuvant chemotherapy is that it may increase the surgeons ability to achieve clear margins. When previously undetected deposits are discovered at surgery or if the tumour is larger than expected, liver resection should be adapted to ensure complete tumour resection wherever possible.

Before the beginning of the liver resection (after abdominal incision), extrahepatic involvement of the abdomen must be excluded by inspection and palpation and frozen section histological examination of suspicious lesions. Intra-operative ultrasonography is suggested to detect and localize any additional metastases but is not mandatory.

A curative resection of the metastases with a clearance of ≥ 1 cm of normal parenchyma should be the aim. However metastases will be considered resectable even if the clearance is less than 1 cm provided complete macroscopic resection of liver metastases is possible. Whether anatomical liver resection or wedge resection or a combination of the two is carried out depends on the localization of the metastases. The surgical technique, including vascular isolation, use of technology is left to each surgeon's discretion. The technique used should be noted on the correct form and blood loss and extent of resection detailed. Post-operative follow up will be recorded and serious complications will be reported within one month after surgery to allow a direct comparison.

Post-operative study treatment should **start 4 weeks** after surgery (not earlier); however, post-operative study treatment may be delayed until 8 weeks after surgery, at the latest. The rationale for any delays must be documented in the CRF.

9.d Other anticancer treatment modalities

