There are no specific drug interactions documented with Cetuximab. However, any agent that may interfere with the immune system of the patient should preferably be avoided except the indicated study regimen and necessary supportive treatment (including Corticosteroids, Antiemetics etc).

St John's Wort is contraindicated for concomitant use with irinotecan. St John's Wort induces the cytochrome P450 isoform CYP3A4 which leads to reduced plasma levels of the active Irinotecan metabolite SN-38.

The following medications may interact with chemotherapy in New EPOC. These medications are not contraindicated but should be avoided unless there is no reasonable alternative:

1. **Allopurinol**: may potentially reduce the effectiveness of 5FU.

11. Trial procedures

11.a Centre approval process

The following documentation must be received by UoSCTU in order for a centre to become an approved New EPOC centre:

- Confirmation of ethics approval (site-specific assessment);
- A copy of the most recent version of the patient information sheets and consent form on local headed paper;
- Confirmation from the MHRA that centres/investigators have been added to the New EPOC CTA;
- Completed delegation log (signature list and delegation of responsibilities);
- Full contact details for all centre personnel;

Once all of this documentation has been received, confirmation of centre approval will be sent to the Principal Investigator at each centre by the trial team at UoSCTU.

11.b Within the week prior to randomisation

- The patient should have a minimum of 24 hours after the initial invitation to participate before being asked to sign the main trial consent form.
- Ensure that the patient understands that they are free to give or withhold permission for the translational studies (single blood sample and use of resected primary colorectal cancer and liver metastases) without affecting their participation in the clinical study.
- History and examination.
- Assessment of performance status.
- Full blood count and biochemistry. Calculate GFR using Cockcroft formula (see Appendix VIII). If the Cockcroft estimate is < 50 ml/min, a measured GFR is required (e.g. by EDTA clearance). Magnesium levels & C Reactive Protein (CRP) should also be recorded.
- Ensure patient has measurable disease (RECIST criteria, Appendix V) and that a baseline CT scan (chest, abdomen, pelvis) has been (or will be) performed **within 4-6 weeks prior to the planned start date for chemotherapy**.

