- Check all other inclusion and exclusion criteria in protocol section 8.

kRAS genotyping

- During the initial clinic visit where the main trial patient information sheet is provided, also provide the patient with the kRAS patient information sheet and answer any questions the patient has regarding the kRAS genotyping.
- Seek appropriate informed consent to conduct kRAS genotyping and ask the patient to sign the kRAS consent form.
- If consent to conduct kRAS genotyping is obtained, request a sample from the patients' primary cancer (paraffin block or biopsy) from the relevant pathology laboratory and send with a copy of the histology report and kRAS genotype request form for kRAS analysis (see Appendix XIV). Any reports sent may only identify patients by their initials, year of birth and the New EPOC site ID number where the patient consented to participate in the trial. Package the sample in the safebox provided according to the requirements described by the University of Southampton Clinical Trials Unit in the investigator information sheet, mark as '**urgent clinical sample**' and send to:

Molecular Genetics Laboratory
Institute of Medical Genetics
Cardiff & Vale NHS Trust
[name]
[name]

- kRAS genotype will be reported by the Molecular Genetics Laboratory in Cardiff within one working week to the University of Southampton Clinical Trials Unit which will subsequently forward results to the relevant trial site.

- Patients who have already been kRAS genotyped locally, and are confirmed as wild -type, please send a copy of the kRAS result to the University of Southampton Clinical Trials Unit prior to randomisation.
- Please also send a tumour block before or after randomisation to Cardiff using the procedures outlined above, in order for quality assurance purposes.

After obtaining written consent to the main trial:

- Patient to complete first QoL forms (see appendices IX and X).
- Confirm with the patient whether they are to receive OxMdG or IrMdG chemotherapy regimen.

11.c Randomisation

Enrolment will only be accepted if current eligibility criteria have been checked, written consent obtained, chemotherapy choice decided (OxMdG or IrMdG) and the current baseline QoL form has been completed.

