- Patients will be randomised to the control or experimental arm by telephone to the MRC Clinical Trials Unit. Randomisation will utilise minimisation and the stratification factors are surgical centre, poor prognostic tumour (yes or no) and prior treatment with Oxaliplatin as adjuvant (yes vs. no). A poor prognostic tumour is defined as having any one or more of the following ≥ 4 metastases (yes or no), N2 disease (yes or no) or poor differentiation at biopsy (if available, if not available the tumour is considered to be not poorly differentiated).
- Complete the first page of the Baseline and Randomisation Form and telephone the MRC CTU on **[name]** (9am – 5pm, Mon-Fri).
- Details will be taken and the patient will be allocated a treatment and trial number. At that point, complete the remainder of the Randomisation Form and fax it to UoSCTU on **[name]**, together with the baseline QoL form and a copy of the signed Consent Form.
- Also at this point, provided the patient has not withheld consent for the translational studies:
 1. Ensure that the patient's pathology details are recorded on the **Randomisation and pre-treatment Form and request the pathology block from the relevant local pathology laboratory using the pathology request form.**
 2. Request stored pathology samples (normal and tumour tissue) from previous resection surgery of the patients' primary colorectal cancer and take 20 ml blood in an EDTA tube (2 tubes required if 10 ml size). Label each sample with the **date of collection and patient details**. Seal the tube(s) in a plastic bag, place in a Royal Mail 'safeBox' provided by UoSCTU and post first-class with a copy of the patient consent form and any histology information available. The address for posting is:

New EPOC Trial Sample laboratory
Cancer Sciences Tissue Bank
[name]
[name]
[name]
[name]

11.d Start of chemotherapy

Treatment should start as soon as possible after randomisation. However, a delay of up to 3 weeks from randomisation to start of treatment (e.g. for venous line insertion) may elapse if clinically acceptable. Patients should still be treated within 4-6 weeks of the cross sectional imaging scan used to assess their disease. If the patient will receive infused 5FU in OxMdG or IrMdG but the line cannot be fitted sufficiently quickly, give the first cycle of treatment as an inpatient.

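### Section 11.b allows the scan that supplies the RECIST baseline to be done after open-label randomisation, so target lesions and their baseline sum can be chosen with the arm known

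*Protocol*

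**What the plan says.** Section 11.b lists the checks for the week before randomisation. One item begins "Ensure patient has measurable disease (RECIST criteria, Appendix V" and goes on to say that the baseline CT of chest, abdomen and pelvis "has been (or will be) performed", with a window of 4-6 weeks counted back from the planned start of chemotherapy. The next item reads "Check all other inclusion and exclusion criteria in protocol section 8".

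The other rules that time this scan also count from treatment:

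- The footnote to the schedule in section 3: "procedure may be performed at screening or baseline but must be within 6 weeks prior to chemotherapy".
- Section 11.d asks for treatment within 4-6 weeks of the scan used to assess disease. It also says that "a delay of up to 3 weeks from randomisation to start of treatment (e.g. for venous line insertion) may elapse if clinically acceptable".
- Appendix V wants the measurements as near to the start of treatment as possible, and no more than 6 weeks before it.

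Several steps at or before randomisation need imaging. Section 8 requires potentially resectable, measurable liver disease without distant extra-hepatic disease. Appendix VI makes contrast CT or MRI mandatory for judging resectability. The minimisation in section 11.c uses a lesion count: "A poor prognostic tumour is defined as having any one or more of the following ≥ 4 metastases". Section 9.c says: "The type and extent of liver resection should be decided at time of randomisation".

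Section 11.c accepts enrolment only once eligibility has been checked, consent obtained, the chemotherapy chosen and the quality of life form completed. A completed baseline CT is not named.

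**The concern.** The title of the trial calls it open label, and the protocol describes no central review of imaging. The RECIST baseline involves judgement: Appendix V lets the assessor select up to 5 target lesions per organ and 10 in all, and the sum of their longest diameters becomes the reference for response. If that selection is made after the arm is known, knowledge of the arm can influence which lesions are followed and how large the starting sum is.

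Two uses of that baseline are exposed. One is pre-operative response, a secondary outcome in section 6. The other is RECIST progression in patients whose metastases are not resected, which is part of the primary outcome for that group.

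The wording also sits badly with the pre-randomisation steps that need imaging. A list that tells the site to make sure of measurable disease, and in the same sentence accepts a scan still to be done, leaves unclear which scan does which job.

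**Working it through.** **The design figure.** The scan rule carries no figure of its own. As context, the plan's 212 target events reproduce from a hazard ratio of 0.68, 80% power and a two-sided 5% level with equal allocation:

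4 × (1.960 + 0.842)² / (ln 0.68)² = 31.4 / 0.1487 ≈ 211.1, rounded up to 212.

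Nothing below alters it.

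**When the scan can fall.** Inputs:

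- d = days from randomisation to chemotherapy, 0 to 21 (section 11.d; section 9.a gives the same limit).
- s = days from scan to chemotherapy, from the window.
- Scan day relative to randomisation = d − s, where negative means before.

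| Reading of the window | s | Earliest scan | Latest scan |
|---|---|---|---|
| Outer limit of 6 weeks (section 3, Appendix V) | 0 to 42 | 0 − 42 = −42 | 21 − 0 = +21 |
| Outer limit of 4 weeks | 0 to 28 | 0 − 28 = −28 | 21 − 0 = +21 |
| Literally 4 to 6 weeks before chemotherapy | 28 to 42 | 0 − 42 = −42 | 21 − 28 = −7 |

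On either outer-limit reading, a baseline CT up to 21 days after allocation complies. On the literal reading it cannot follow allocation at all.

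**Which reading fits the text.** On the literal reading, the scan must already be at least 7 days old at randomisation. A check made in the final week could then hardly ever find a compliant scan still to come, so the future-tense alternative in 11.b would have almost no meaning. That reading would also make a scan taken close to treatment a deviation, whereas Appendix V prefers exactly such a scan. The outer-limit reading agrees with section 3 and Appendix V.

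**Is there an ordering rule elsewhere?** Section 8 ties the eligibility blood tests to randomisation (within 1 week before it). None of the four places that time the scan (section 3, 11.b, 11.d, Appendix V) does so. The schedule marks CT and RECIST in the screening column, but randomisation is marked in that column too, so it sets no order.

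**What depends on the baseline.** Partial response needs a fall of at least 30%, so the threshold is 0.70 × the baseline sum: 70 mm for the 100 mm baseline in the Appendix V example. Each millimetre in the baseline moves the threshold by 0.7 mm. Progression is judged against the smallest sum recorded. The baseline is that reference when there has been no shrinkage, and the choice of target lesions carries through every later sum.

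**The case against.** The strongest reply is that the protocol settles everything needed for entry before the arm is known. Measurable disease is to be ensured in the week before randomisation, all other criteria are checked in the same list, enrolment is refused until they have been, and minimisation cannot run without the lesion count. Fixing the extent of resection at randomisation confirms that imaging is expected by then. All of this stands.

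A reader might therefore infer from 11.b that entry, resectability or the minimisation factor can be judged with the arm known, or that patients could be excluded after randomisation. The protocol does not support this. A site that randomised with no staging imaging would breach 11.b and 11.c, and section 9.e keeps every randomised patient evaluable for intention to treat.

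It can also be said that the scan still to be done may simply fall later in the same week, before randomisation, and that the baseline visit in section 3 is probably the randomisation visit, since the footnote's limit of under 3 weeks from baseline to week 1 resembles the 3-week limit from randomisation to treatment. That may be what was meant, but no section says so.

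Finally, the effect on the primary outcome is limited. In resected patients, section 6 counts recurrence or progression after surgery, or death, so the baseline sum matters little there. This also stands and narrows the exposure to the two uses named above. As for who reads the RECIST scans, the protocol does not say; Appendix VI assigns only resectability to local practice.

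**Conclusion.** The point holds in a limited form. The rule times the baseline CT only against chemotherapy and accepts it as outstanding at the pre-randomisation check. On the reading that section 3 and Appendix V support, the RECIST baseline may be measured up to 21 days after open-label allocation. Eligibility and the metastasis count must still be settled beforehand, but the protocol does not say that the scan used for them must also be the RECIST baseline.

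The possible bias lies in target-lesion choice and the baseline sum. It affects pre-operative response and RECIST progression in unresected patients. Its size cannot be given: the protocol offers no basis for how many of the 288 patients would be scanned after randomisation, or how far readings would shift. The conclusion assumes that the window is an outer limit; under the strictly literal 28 to 42 days, the gap closes. No sample size, power or alpha figure changes.

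**What to change.** - **Section 11.b:** delete the bracketed future-tense alternative. Require that the baseline CT has been performed, and that the target lesions and their sum of longest diameters have been recorded, before randomisation.
- **Section 11.c:** add this to the conditions for accepting enrolment.
- **Sections 11.b and 11.d:** reconcile their 4-6 week wording with the 6-week limit in section 3 and Appendix V, so that one window applies throughout.

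This is a change of wording and needs no extra scan for most patients. A CT done up to 3 weeks before randomisation still meets the 6-week limit after the full permitted delay (3 + 3 = 6 weeks). The cost is that a few randomisations would wait some days for a scan that was already planned.

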 - Patients who are thought by the hepatic surgeon to be suboptimally resectable are included. This will normally include patients, for instance, who have potentially resectable disease but in whom compromise of the resection margins is likely. These patients are currently normally treated with pre-operative chemotherapy under NICE guidance. This decision will be at the surgeons discretion.
 - Unidimensionally measurable disease (RECIST criteria, see AAppendix V) to measure pre-operative response.
 - Patients with previously resected liver metastases for whom surgery was performed ≥ 1 year previously.
 - No previous systemic chemotherapy for metastatic disease.
 - adjuvant chemotherapy with 5FU +/- FA, Capecitabine or Oxaliplatin may have been given, if completed > 6 months prior to trial entry.
 - rectal chemoradiotherapy with 5FU +/- FA may have been given, if completed > 1 month prior to trial entry.
- WHO performance status (PS) 0, 1 or 2 (see AAppendix VII) and considered by responsible consultant to be fit to undergo combination chemotherapy.
 - Baseline laboratory tests (within 1 week prior to randomisation):
 - neutrophils $\geq 1.5 \times 10^9/l$ and platelet count $\geq 100 \times 10^9/l$
 - serum bilirubin $\leq 1.25 \times$ upper limit of normal (ULN), alkaline phosphatase $\leq 5 \times$ ULN, and serum transaminase (either AST or ALT) $\leq 2.5 \times$ ULN
 - estimated creatinine clearance (Cockcroft; Appendix VIII) >50 ml/min or measured GFR (EDTA clearance) >50 ml/min.
 - All patients must be aged 18 years or older.
 - For women of childbearing potential, negative pregnancy test and adequate contraceptive precautions. Adequate contraception for men.
 - Written informed consent.
 - Consent to allow surplus pathological material to be analysed for translational research projects (*patients may decline participation in this supplementary component and still participate in the main trial*).

Exclusion criteria

- Patients who are unfit for the chemotherapy regimens in this protocol, e.g.:
 - severe uncontrolled concurrent medical illness (including poorly-controlled angina or very recent MI, i.e. in previous 3 months) likely to interfere with protocol treatments.
 - Any psychiatric or neurological condition which is felt likely to compromise the patient's ability to give informed consent or to comply with oral medication.
 - Partial or complete bowel obstruction.
 - Pre-existing neuropathy (> grade 1).

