18. Analysis plan and statistics

This 2 arm trial will compare the experimental arm (OxMdG-C/IrMdG-C, ARM B) against the control (OxMdG/IrMdG, ARM A).

Sample Size Calculation

The original EPOC trial (EORTC 40983) compared patients having surgery alone to patients being treated with pre and post operative chemotherapy with FOLFOX⁴². It assumed that chemotherapy may increase the median progression free survival by 40% from 16 months to 22.4 months. The power calculation study required 330 patients (165 in each arm) and 364 were actually recruited. The study demonstrated that peri-operative FOLFOX improved PFS and is compatible with major liver surgery⁴². This trial studied a group of patients with favourable liver metastases (4 lesions or less, mainly metachronous presentation). The group being studied in the current proposal has a considerably worse prognosis^{1-10, 46} as it includes patients with synchronous presentation and with sub optimal operability. An open study of such a group of patients treated with FOLFOX chemotherapy and surgery revealed a median progression free survival of around 17 months⁴⁷. The current proposal will also recruit a cohort of patients with metachronous disease who have received adjuvant Oxaliplatin. The survival of this group is less good than those patients treated with 5FU alone. However, metachronous disease patients suitable for FOLFOX have improved PFS compared to synchronous disease patients. Considering published data and the target patient population for this trial the expected median PFS for the control group is 15 months. The Crystal study⁴⁹ randomly assigned 599 patients with epidermal growth factor receptor-positive colorectal cancer with unresectable metastases to receive FOLFIRI either alone or in combination with Cetuximab. The results found the overall hazard ratio observed for progression free survival among 348 patients with wild-type-KRAS tumours was 0.68 (95% CI, 0.5 to 0.94). The results from the Crystal study have been used to power the New EPOC trial because it is internationally accepted as the best demonstration of Cetuximab in advanced colorectal cancer and if in New EPOC an effect less than this is observed it would be questionable as to whether it would be considered clinically meaningful. Further, bearing in mind the cost of antibody treatment, a hazard ratio greater than this would not justify its routine use. Using a hazard ratio of 0.68, assuming 80% power, a 5% 2-sided significance level and 5% loss to follow up by 2 years the total number of patients required with kRAS wild type genotype in the primary tumour is 268 (134 in each arm). This means the total sample size required for New EPOC is 288. This ensures the 20 patients for whom their kRAS status is unknown as they were recruited before the protocol amendment are replaced. The total sample size 268 patients with kRAS wild type genotype in the primary tumour is powered to detect 212 target events (disease progression). The sample size calculation was performed using ART version 1.07 in STATA and assumed recruitment would take place over 3 years with 5 years of follow up. Baseline survival probabilities from EPOC were also used in the calculation. This assumed progression free survival at 1 year, 2 years and 3 years was 67%, 46% and 35% respectively.

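### The primary PFS model is fixed as unadjusted although section 18 itself names synchronous presentation and suboptimal operability as prognostic; pre-specified adjustment would recover up to about 10 points of power

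*Protocol*

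**What the plan says.** Section 11.c randomises by minimisation: "the stratification factors are surgical centre, poor prognostic tumour (yes or no) and prior treatment with Oxaliplatin as adjuvant (yes vs. no". The second factor is a composite: "A poor prognostic tumour is defined as having any one or more of the following", namely four or more metastases, N2 disease or poor differentiation. Timing of the metastases and operability are not in it.

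Section 18 (Sample Size Calculation) argues that this population fares worse than that of the original EPOC trial because "it includes patients with synchronous presentation and with sub optimal operability". It adds that "metachronous disease patients suitable for FOLFOX have improved PFS compared to synchronous disease patients". It also describes "a cohort of patients with metachronous disease who have received adjuvant Oxaliplatin", whose outlook it calls less good; that feature is a minimisation factor.

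Both unlisted features are settled at entry. Section 8 lists synchronous and metachronous patients separately, and states: "Patients who are thought by the hepatic surgeon to be suboptimally resectable are included".

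Section 18 (Initial analysis plan) makes the primary Cox comparison unadjusted. Sensitivity analyses may adjust for confounders if imbalances happen to arise; no covariates are named. The planned combined analysis with COIN, by contrast, is adjusted for the stratification factors.

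**The concern.** The protocol treats both features as prognostic for its primary endpoint, then leaves them out of the primary model. In a Cox model, omitting prognostic covariates attenuates the treatment hazard ratio towards 1 even when the arms are perfectly balanced on them. The result is lost power in a trial planned at 80%. Adjustment that is optional and triggered by observed imbalance does not recover this, because the attenuation does not depend on imbalance. It also leaves the covariates to be chosen after the data are seen. Since the protocol itself fixes the primary model as unadjusted, this is not a detail left open for the statistical analysis plan.

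**Working it through.** **1. The plan's own figure.** Inputs from section 18: "Using a hazard ratio of 0.68, assuming 80% power, a 5% 2-sided significance level and 5% loss to follow up by 2 years". Schoenfeld events = 4(1.960 + 0.842)² / (ln 0.68)² = 31.4 / 0.1487 = 211.1, rounded up to 212, as stated. Power at 212 events is 0.802. The patient total also agrees: 268 + 20 = 288.

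**2. Power with and without the covariates, section 18 design.** 268 patients; control PFS 67%, 46% and 35% at 1, 2 and 3 years, with the third-year hazard carried forward (assumption); 3 years' accrual plus 5 years' follow-up; 5% loss by 2 years; treatment hazard ratio 0.68 within strata. Assumed, because the protocol gives no values: 50% synchronous, 30% suboptimal, independent of each other, each with the prognostic hazard ratio shown. Monte Carlo error is about 1 point.

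| Prognostic HR of each feature | Unadjusted power | Adjusted power |
|---|---|---|
| 1.3 | 77% | 78% |
| 1.5 | 74% | 78% |
| 2.0 | 68% | 78% |

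The ceiling is 78% rather than 80% because, with loss continuing at the same rate, about 76% of patients have an event: 0.76 × 268 ≈ 204, not 212.

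**3. The same comparison at exactly 212 events** (exponential PFS, control median 15 months, allocation not balanced on the two features; 3000 runs per row).

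| Prognostic HR | Mean log HR, unadj. / adj. | Model SE, unadj. / adj. | Power, unadj. / adj. |
|---|---|---|---|
| 1.3 | −0.381 / −0.390 | 0.139 / 0.140 | 0.80 / 0.81 |
| 1.5 | −0.369 / −0.387 | 0.139 / 0.140 | 0.76 / 0.80 |
| 2.0 | −0.340 / −0.386 | 0.139 / 0.140 | 0.70 / 0.80 |

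The standard error does not fall with adjustment. The gain comes from removing attenuation: at 2.0, the unadjusted model averages exp(−0.340) = 0.71 where the within-stratum value is 0.68.

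**4. If 0.68 is instead the marginal hazard ratio.** At prognostic HR 2.0 the attenuation ratio in step 3 is 0.340 / 0.386 = 0.881, so the conditional log HR is about −0.386 / 0.881 = −0.438. Unadjusted power = Φ(0.386/0.1385 − 1.96) ≈ 0.80; adjusted power = Φ(0.438/0.140 − 1.96) ≈ 0.88. The plan then keeps its 80%, and adjustment adds about 8 points.

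**5. What adding the features to the minimisation would do.** Keeping the unadjusted model, allocation left to chance versus balanced on both features:

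| Prognostic HR | Model SE | Empirical SD | Power |
|---|---|---|---|
| 1.3 | 0.139 v 0.139 | 0.139 v 0.135 | 0.80 v 0.78 |
| 1.5 | 0.139 v 0.139 | 0.139 v 0.132 | 0.76 v 0.78 |
| 2.0 | 0.139 v 0.139 | 0.136 v 0.128 | 0.70 v 0.73 |

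**6. Size of a chance imbalance.** SD of the arm difference at 50% prevalence = √(2 × 0.5 × 0.5 / 134) = 6.1 points, and the chance of more than 10 points is about 10%. At 30% prevalence the SD is 5.6 points and the chance about 7%. A 10-point imbalance multiplies the hazard ratio by 1.3^0.1 = 1.03, 1.5^0.1 = 1.04 or 2.0^0.1 = 1.07.

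**The case against.** A reader might infer that the minimisation list is the fault and should be extended. The documents and the arithmetic do not support that. Step 5 shows the reported standard error unchanged and at most about 3 points of power gained. A short list that already includes surgical centre is defensible for 268 to 288 patients. Section 14 expected recruitment to end in December 2012, so a new factor would probably apply to nobody.

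A reader might also infer that these are the only prognostic features section 18 names, or the strongest, and that they are balanced by chance alone. Section 18 names adjuvant oxaliplatin too, which is balanced. It describes that cohort as metachronous, so the factor captures presentation in part, though metachronous patients without oxaliplatin still fall with synchronous ones. Four or more metastases may overlap with operability. No effect sizes are given, so no ranking is possible.

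Three further points stand. Chance imbalance is not bias, and its likely effect (factors of 1.03 to 1.07) is well within a standard error of about 0.14 on the log scale. The 0.68 comes from an overall published hazard ratio, so it may be marginal, in which case the planned 80% is not lost. Finally, at a prognostic hazard ratio of 1.3 the gain is negligible. None of this removes the case for adjustment, which adds some power on either reading of 0.68 (step 4).

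**Conclusion.** The point holds as a missed gain in power from an unadjusted primary model, not as an error of randomisation. The treatment comparison is valid, and the 212 events and 288 patients reproduce. Under the stated assumptions, pre-specified adjustment is worth about 1 point of power if each feature has a hazard ratio of 1.3, about 4 points at 1.5 and about 10 points at 2.0. The 50% synchronous assumption is the most favourable to the point, because p(1 − p) is largest there. Section 4 says the trial targets mainly synchronous disease; at 70% to 80% synchronous, p(1 − p) falls from 0.25 to 0.21 or 0.16 and the gain would be smaller. The size therefore depends on how prognostic the features are, which the protocol asserts but does not quantify.

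**What to change.** In section 18, specify the primary PFS Cox model as adjusted for synchronous versus metachronous presentation and, where the surgeon's pre-randomisation judgement was recorded, suboptimal resectability (yes/no), alongside the minimisation factors. Report the unadjusted hazard ratio as supportive. Name the covariates and settle how missing values are handled before any comparative PFS data are seen. Leave the minimisation list as it is.

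The cost is small: two covariates beyond the minimisation factors, against about 200 events. The hazard ratio becomes conditional on these covariates, so it is not directly interchangeable with an unadjusted published value; the supportive unadjusted estimate covers that comparison. The contents of the Baseline and Randomisation Form are not shown, so whether the resectability judgement was captured before allocation has to be checked. If it was not, adjust for presentation only, since a judgement reconstructed after allocation in an open-label trial could be influenced by treatment.
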